7. STUDY PROCEDURES

7.1 Schedule of Events

	Screening Visit	Baseline	Month 1 Visit	Month 3 Visit	Month 6 Visit
Assessments	Day -14 to -7 days ±2 days	Visit Day 0	±3 days	± 7 days	± 7 Days
Informed Consent	Х		(M)		
Evaluation of Enrollment Criteria	х	х			
Demographics	Х				
Vital Signs	Х				
History Joint OA (Index & Contralateral for wrist, elbow and shoulder)	х				
Medical History	х				
Concomitant Medication	х	х	X	х	х
Assess non-drug therapies	х	х	Х	Х	Х
Adverse Event Assessment		Х	X	Х	Х
Collect & Review Subject Diary		Х	X	Х	х
Rescue Medication usage / washout		х	X	х	х
Patient Global Assessment (PGA)	Х	Х	X	х	х
DASH index index shoulder	Х	Х	X	Х	Х
Index and Contralateral Shoulder Joints Pain (0-10 Numeric Rating Scale)	х	х	х	х	x
Physical Evaluation of Index and Contralateral Shoulder Joints	х	x	х	Х	X
Study Injection		х			
Dispense Subject Diary		х			

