7.2 Procedure Description

7.3 Screening Visit (Day -14 to -2 days)

The following screening and eligibility data will be collected.

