7.3.9.2 Rescue Medications

Acetaminophen/paracetamol (up to a maximum of 4.0 grams per day per the package insert or as per regional limitations) will be allowed as the rescue medication for the treatment of Osteoarthritis for the duration of the study. At least forty-eight hours prior to the Baseline Visit, 1, 3 and 6 Month Assessments the subject should discontinue use of the rescue medication.

The subject should be instructed to track pill usage daily to convey accurate pill counts at follow-up assessments.

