7.4 Baseline Visit: Treatment Visit (Day 0)

The Baseline Visit (Day 0) will occur 7 to 14 days after the Screening Visit to allow for rescue medication washout. The injection will occur at this Baseline visit along with the following activities:

Before Treatment Injection

- Concomitant Medications
- Current non-drug therapies
- Confirm Medication Washout
 - If subject did not complete medications washout, reschedule the visit to allow washout to be completed.
- Patient Global Assessment (PGA)
- DASH index shoulder
- Index & Contralateral Shoulder Joint Pain (NRS Scale)
 - o Confirm Baseline Inclusion & Exclusion Criteria for NRS pain
- Physical Exam of Index and Contralateral Shoulder Joints

Treatment Procedure

The Treating Physician will always perform the Study Injection to the index joint as standard of care dictates.

Intra-articular injection of the shoulder joint should be conducted under fluoroscopic or ultrasound guidance. Guidelines for the injection procedural steps are provided below. Modifications to this technique should be recorded in the CRF

- Patient may be sitting or supine as required.
- Prep the skin at injection site with 1% betadine solution or equivalent.
- Peri- articular injection site anesthesia of lidocaine or topical refrigerant anesthetic (e.g. ethyl

chloride) may be utilized.

- Use fluoroscopic or ultrasound guidance to insert 18-22 1 cm lateral and 1 cm cephalad to the coracoid process. Insert the needle directed 20° medially and 60° caudally to enter the joint.
- Insert needle until resistance against the articular surface and then withdraw the needle 1-2 mm.
- If using fluoroscopic guidance, a small amount of fluoroscopic contrast agent (0.5 to 1.0 ml) should be injected through the needle to verify intra-articular placement.
- If using ultrasound guidance, a small volume of air (up to 0.5 ml) may be injected to verify IA positioning.
- If pooling of the contrast agent or air around the needle tip is observed, the needle should be repositioned.
- When contrast agent or air is successfully injected into the joint, intra-articular placement is confirmed.
- Following confirmation of intra-articular needle placement, the joint may be aspirated to remove synovial fluid.
 - o Confirm the Baseline Exclusion for synovial aspirate.
- 4 ml of MONOVISC is injected into the joint.
- Intra-articular anesthetic should NOT be administered as part of the injection procedure.

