#### 4.1.3.6 Reduction in Pain Medication usage at 1 Month, 3 Months and 6 Months.

The reduction from screening -baseline period in the mean reduction of medication usage per day between each visit will be tabulated and 95% confidence intervals will be calculated.

Number of subjects taking rescue medication between each visit will be tabulated.

This will be estimated using PROC MEANS. The results will tabled like the primary endpoint in section 4.1.2.1.

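### The reference period for the medication-usage endpoint has no assured daily paracetamol record, no single length and no stated per-day denominator

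*Protocol*

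**What the plan says.** Reduction in medication usage from baseline to 6 months is a secondary endpoint (Protocol 6.2). SAP 4.1.3.6 sets its reference: "The reduction from screening -baseline period in the mean reduction of medication usage per day between each visit will be tabulated", with 95% confidence intervals.

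On the record of use, Protocol 7.1 places "Dispense Subject Diary" in the Baseline column alone. It places "Collect & Review Subject Diary" and "Rescue Medication usage / washout" at Baseline and at Months 1, 3 and 6. Section 7.3.9.2 adds: "The subject should be instructed to track pill usage daily to convey accurate pill counts at follow-up assessments". Section 7.3.9.6 says that subjects receive a diary but names no visit.

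On the length of the period, the protocol gives three versions:

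- 7.1: "Day -14 to -7 days ±2 days"
- 7.3 (heading): "Screening Visit (Day -14 to -2 days"
- 7.4: Baseline "will occur 7 to 14 days after the Screening Visit to allow for rescue medication washout"

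Section 7.3.9.2 also requires at least 48 hours without paracetamol before Baseline and before each follow-up assessment.

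**The concern.** Every reduction reported for this endpoint is a difference from one short pre-treatment period. Paracetamol here is as-needed rescue medication, so a good estimate of use per day needs a daily record on both sides of the injection. A site that follows the dispensing mark hands out the first diary on the day of injection, and a daily record not started at Screening cannot be made afterwards.

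The length of the period matters for a second reason. Expressing use per day does not by itself make a short reference comparable with a long follow-up interval, because each ends with the same compulsory paracetamol-free stretch. Two days are a sizeable part of one or two weeks and a trivial part of three months. Depending on how the denominator is defined, the comparison can be shifted by the calendar alone, and by different amounts for subjects screened at different distances from Baseline.

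**Working it through.** **No planned figure to reproduce.** The documents give no expected size for this endpoint. The sample size of 15 (Protocol 9.1) concerns the primary NRS t-test and does not enter here.

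**The record, source by source**

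| Source | Screening to Baseline | Follow-up |
|---|---|---|
| 7.1, diary dispensed | no mark at Screening | one mark, at Baseline |
| 7.1, diary collected | marked at Baseline | marked at Months 1, 3, 6 |
| 7.3.9.2, daily pill tracking | Baseline not named | named |
| 7.4 and 7.6 visit lists | 7.4 has no diary or rescue-use item, only a washout check and concomitant medications | 7.6 has both items |
| 7.3.9.3, medication log | from consent: dose, frequency, start and stop dates | same |

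The schedule contradicts itself: a diary cannot be collected at Baseline if the first is issued there. Section 7.3.9.6 is numbered under the Screening Visit, which suggests issue at Screening. But the neighbouring subsections of 7.3.9 hold rules for the whole study, so its position does not settle the matter. The log and the rescue use asked at Baseline support an average, not a daily count.

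**The length.** The interval of 7 to 14 days in 7.4 lies inside all three windows, so it is used below.

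**Effect of the washout under an all-days denominator**

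Inputs and assumptions:

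- Washout of 2 days before each visit (7.3.9.2), with no paracetamol taken in it.
- Constant use *u* on every permitted day, before and after injection.
- Follow-up intervals taken as 30, 61 and 91 days (assumed calendar lengths).
- Use per day = total in the interval / all days in the interval. The SAP does not state this.

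For an interval of *d* days, the washout share is 2/*d* and the recorded use per day is *u* × (*d* − 2)/*d*.

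| Interval | *d* | Washout share | Recorded use / *u* |
|---|---|---|---|
| Reference, longest under 7.4 | 14 | 14.3% | 12/14 = 0.857 |
| Reference, shortest under 7.4 | 7 | 28.6% | 5/7 = 0.714 |
| Baseline to Month 1 | 30 | 6.7% | 28/30 = 0.933 |
| Month 1 to Month 3 | 61 | 3.3% | 59/61 = 0.967 |
| Month 3 to Month 6 | 91 | 2.2% | 89/91 = 0.978 |

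Apparent change in the Month 3 to Month 6 interval when true use is unchanged:

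- 14-day reference: 0.978 − 0.857 = 0.121, a rise of 12% of *u*; relative to the reference, 0.121/0.857 = 14%.
- 7-day reference: 0.978 − 0.714 = 0.264, a rise of 26% of *u*; relative to the reference, 0.264/0.714 = 37%.

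As an illustration, with *u* = 2 g (assumed) the reference reads 1.71 or 1.43 g/day and Month 6 reads 1.96 g/day. The apparent rises are 0.24 and 0.53 g/day from unrounded values.

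Put the other way, a true fall on permitted days of 1 − 0.857/0.978 = 12% (14-day reference) or 1 − 0.714/0.978 = 27% (7-day reference) would show as no change.

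**With permitted days as the denominator**, each ratio becomes (*d* − 2)/(*d* − 2) = 1 and the apparent change is zero for every *d*.

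**The case against.** The case against has real force on several points.

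- *The diary was plainly meant for Screening.* Probably so, since 7.1 collects one at Baseline; a misplaced or missing mark is the likeliest explanation. A reader might infer that no pre-treatment record will exist, and the documents do not support that. What stands is that the record is not assured, because a site can follow the dispensing mark as written.
- *The endpoint is an average, and an average can be had.* This is true. The log, the rescue use asked at Baseline and the site-supplied paracetamol (11.1) could all contribute, so it would be wrong to infer that the endpoint cannot be computed. But 11.1 names no supply visit, 7.3.9.2 ties pill counts to follow-up, and a log of dose and frequency is a coarse measure of as-needed use. The two sides of the difference would be measured differently.
- *The washout effect is not demonstrated.* Correct: it depends on the all-days denominator. That is the natural reading of usage per day between visits, but the SAP is silent.
- *Much shorter reference periods look possible.* A reader might infer this from the tolerance in 7.1 and the heading of 7.3. Such cases would have to override the explicit sentence in 7.4 and still meet the seven-day stop of other analgesics (6.6.1, criterion 7). Section 7.4 also reschedules subjects whose washout is incomplete. No size is attached to them here.
- *Follow-up might go unrecorded after Month 1.* A single dispensing mark invites that inference, but 7.1, 7.3.9.1 and 7.6 call for diary review at the follow-up visits. The re-issue is merely unstated.
- *The stakes are limited.* SAP 4.1.3.6 states no hypothesis and asks for estimates and confidence intervals, though the table layout it borrows carries a p-value row. The washout effect also cannot create a false benefit.

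**Conclusion.** The point holds as an inconsistency worth correcting before data are collected. The reference period has no assured daily paracetamol record and no single length, and the SAP leaves the per-day denominator open.

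On the 7-to-14-day interval, with constant use on permitted days and averaging over all days, unchanged use would appear at Month 6 as a rise of about 14% to 37% relative to the reference (12% to 26% of permitted-day use). The figures are conditional on those assumptions: with permitted days as the denominator they are zero. Where the effect occurs, it understates a benefit.

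The reach is one secondary endpoint. The primary NRS, the PGA and the sample size are unaffected. A reader might also infer damage to the Baseline DASH because of its one-week recall, but nothing in the documents establishes a direction or size, and none is claimed.

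**What to change.** 1. **Diary (Protocol 7.1, 7.3.9.6, 7.4, 7.3.9.2).** Dispense at Screening; re-issue at Baseline, Month 1 and Month 3; collect each diary at the next visit. Add diary collection and rescue-use assessment to the 7.4 list, both of which 7.1 already marks at Baseline. Name Baseline alongside the follow-up assessments in the pill-tracking instruction.
2. **Window (Protocol 7.1 and 7.3).** Adopt the 7.4 interval, Screening 7 to 14 days before Baseline, and remove the other two versions.
3. **Denominator (SAP 4.1.3.6).** Define use per day over permitted days, excluding the 48 hours before each visit from both numerator and denominator. The exclusion from the numerator matters because paracetamol taken during the washout would otherwise count without its days. The washout is a minimum, so a subject who stops earlier will still contribute zero-use days; these can be left as recorded.

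The cost is protocol wording, one SAP sentence, and diaries handed out one visit earlier and re-issued. No visits, subjects or tests are added. A subject who would have been injected sooner than seven days after Screening waits until day 7. For anyone already past Baseline without a Screening diary, the reference can come only from the rescue use asked at that visit and the medication log, and should be flagged as such in the table.

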7.2 Procedure Description

7.3 Screening Visit (Day -14 to -2 days)

The following screening and eligibility data will be collected.

7.3.1 Informed Consent Form

The subject must sign the Informed Consent Form (ICF) prior to enrollment or undergoing study treatment.

7.3.2 Inclusion / Exclusion Criteria

Confirm subject eligibility against the inclusion and exclusion criteria.

7.3.3 Demographics

The following demographic information will be collected at the Screening Visit:

- Age
- Gender
- Race
- Height
- Weight
- Index joint left / right
- Index / Contralateral Shoulder Joint OA Grades

7.3.4 Vital Signs

Patient will have vital signs assessed.

- Blood pressure
- Pulse
- Temperature

7.3.5 History of Joint Osteoarthritis

Subject's history of osteoarthritis including prior treatments for both index and contralateral wrist, elbow and shoulder joints.

7.3.6 Medical History

The relevant medical history of the Index and Contralateral wrist, elbow and shoulder joints will include, but is not limited to, an assessment of:

- History of trauma in the joints
- History of surgery in the joints
- History of injections to treat pain in the joints
- History of other treatments in the joints including failed prior treatments including but not limited to corticosteroid injection, HA injection, acupuncture, RICE (Rest, Ice, Compression, Elevation), NSAIDS.

7.3.7 Pain Assessment

Patient reported Pain of the index and contralateral shoulder joints will be measured with a Numerical Rating Scale (NRS).

7.3.8 Physical Evaluation of Index & Contralateral Shoulder Joints

The Investigator will perform the physical evaluation of the index and contralateral shoulder joints at the time points included in Schedule of Events, and will include the following assessments:

- Appearance of redness or swelling
- · Assessment of pain upon palpation of the joints
- Assessment of comorbidities at the joints

7.3.9 Medications

Medications that the subject may have been taking prior to study enrollment for conditions unrelated to the treatment of osteoarthritis, other than analgesics including NSAIDs, may be continued as long as they will not interfere with study assessments. Low dose aspirin (81 mg) used for cardiovascular protection is allowed if a stable regimen is maintained for the duration of the study.

7.3.9.1 Restricted Medications

All analgesics other than acetaminophen/paracetamol are prohibited during the study. This includes, but is not restricted to, NSAIDs, opioids and topical agents for treatment of osteoarthritis of index joint. Topical corticosteroids are allowed at any other site other than the index joint. The analgesic medication use will be monitored at each subject assessment through review of the subject diary.

7.3.9.2 Rescue Medications

Acetaminophen/paracetamol (up to a maximum of 4.0 grams per day per the package insert or as per regional limitations) will be allowed as the rescue medication for the treatment of Osteoarthritis for the duration of the study. At least forty-eight hours prior to the Baseline Visit, 1, 3 and 6 Month Assessments the subject should discontinue use of the rescue medication.

The subject should be instructed to track pill usage daily to convey accurate pill counts at follow-up assessments.

7.3.9.3 Concomitant Medications

A medication is considered concomitant if taken after signing the ICF and up to and including the last follow-up assessment. Data on medications will include: medication name, dose, unit, route, frequency, start date, stop date, indication and whether the medication was taken for an AE.

At each study assessment, the subject will be asked about any new medications that were started since the last assessment. Indications for any new medications started after the study treatment will be recorded as AEs, unless the medications are administered for a pre-existing condition.

7.3.9.4 Non-Drug Therapies

Non-drug therapies are any therapies used to treat the index joint that are not a pharmaceutical

Version 2.0 14 Aug 2019 Confidential Page 17 of 38

treatments.

7.3.9.5 Joint Function Assessment

Subjects will receive assessment of the respective joints for functional use.

7.3.9.6 Subject Diary

Subjects will receive diary for to record rescue medications and concomitant medications.

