5.3 Precautions

The following precautions are cited in the package insert (AML 500-263/E):

- Those precautions normally considered during injection of substances into joints are recommended.
- Only medical professionals trained in accepted injection techniques for delivering agents to joint spaces should inject sodium hyaluronate for this application.
- The amount of Monovisc necessary to be injected depends on specific site and patient
 anatomy and needs to be defined by the medical professional performing the procedure. An
 excess quantity of sodium hyaluronate should not to be used and the patient should be
 monitored closely.
- The synovial space should not be overfilled.
- If pain increases during the injection procedure, the injection should be stopped and the needle withdrawn.
- Transient pain or swelling may occur after the intra-articular (IA) injection.
- As with any invasive joint procedure, it is recommended that patients avoid strenuous or prolonged (i.e., more than one hour) weight-bearing activities such as running or tennis within 48 hours following the intra-articular injection.
- Pregnancy: The safety and effectiveness of the use of MONOVISC® in pregnant women has not been tested.
- **Nursing Mothers:** It is not known if MONOVISC® is excreted in human milk. The safety and effectiveness of the use of the product in lactating women has not been tested.
- **Pediatrics**: The safety and effectiveness of the use of MONOVISC® in pediatric patients (≤ 21 years of age) has not been tested.

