- Following the injection, the patient should be advised to maintain a low level of physical activity for the next 48 hours. Cold therapy and/or acetaminophen/ paracetamol may be prescribed to address short term injection site pain.

Post-Treatment Assessments and Instructions

Prior to leaving the clinic, the subject should be evaluated for local and non-local AEs. All post-treatment signs and symptoms that are unexpected should be recorded as AEs. The expected appearance of the index joint should be discussed with the subject with a request that all unexpected symptoms be reported to a member of the study team.

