7.5 Follow-Up Visits

All study subjects will have follow-up visits at 1, 3 and 6 Months after Baseline to evaluate the joint pain score and to assess adverse events.

The subject should be contacted at least 48 hours prior to their scheduled assessments to be reminded of the required assessment (and applicable wash out period) and to schedule the date and time of contact. At least three documented attempts will be made to contact the subject in order to accomplish maximum subject compliance with the follow-up schedule.

The following tests will be performed at the follow-up visits at 1, 3, and 6 months.

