#### 2.0 Study Design

This is a prospective, post market clinical follow-up (PMCF) multi-center, open-label study to evaluate the residual risk of injections of MONOVISC for relief of pain in patients with a diagnosis of an osteoarthritic hip joint (MON 18-01), shoulder joint (MON 18-02), and ankle joint (MON 18-03).

The subjects in each of these study will be patients with a diagnosis of osteoarthritic (OA) joint who the investigator determines are appropriate candidates for treatment with a viscoelastic injection of MONOVISC.

In each study, up to 25 subjects will be enrolled at up to 20 investigational sites in the EU. Subject participation will last approximately 6 Months, with visits scheduled at Screening, Baseline, 1 month, 3 month and 6 months.

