### **4.1.3.4** Responder index based on OMERACT- OARSI responder index at 1 Month, 3 Months and 6 Months.

The response rate for each time point will be tabulated and exact 95% confidence intervals will be calculated.

This will be estimated and tested using PROC FREQ with the BINOMIAL option. The results will be displayed similar to the format below.

Summary of the OMERACT-OARSI Responder Rates at each visit and each protocol.

| Parameter               | 1 Week | 1 Month | 3 Months | 6 Months |
|-------------------------|--------|---------|----------|----------|
| Estimate n/N (%)        |        |         |          |          |
| 95% Confidence Interval |        |         |          |          |

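### No scheduled AE enquiry falls between the Day 0 pre-discharge check and Month 1, and the diary is described for medications only, so transient injection-site reactions arising after discharge may be under-recorded

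*Protocol*

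**What the plan says.** **Visits.** Protocol 7.5: "All study subjects will have follow-up visits at 1, 3 and 6 Months after Baseline". The Schedule of Events (7.1) has AE assessment at Baseline and at Months 1, 3 and 6, with nothing between Baseline and Month 1.

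**Injection day.** Protocol 7.4: "Prior to leaving the clinic, the subject should be evaluated for local and non-local AEs". The same paragraph directs that unexpected signs and symptoms be recorded as AEs. It has the expected appearance of the joint discussed with the subject, "with a request that all unexpected symptoms be reported to a member of the study team".

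**AE rule.** Protocol 8.1.1 requires every AE during or after injection to be recorded, whatever its severity or relationship, with its duration. It names pain, swelling, erythema, bleeding and infection at the injection site as complications. Each assessment covers the time since the previous one.

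**Diary.** Protocol 7.3.9.6: "Subjects will receive diary for to record rescue medications and concomitant medications".

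**Expected reactions.** Protocol 5.3: "Transient pain or swelling may occur after the intra-articular (IA) injection". Protocol 4.2 lists temporary pain, swelling, tenderness and stiffness among the risks of shoulder injection.

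**SAP shells.** The primary endpoint table (SAP 4.1.2.1) opens with a 1-week block, and the responder table (SAP 4.1.3.4) has columns "1 Week | 1 Month | 3 Months | 6 Months". SAP 2.0 describes all three studies "with visits scheduled at Screening, Baseline, 1 month, 3 month and 6 months".

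**The concern.** Protocol 6.5 gives evaluation of the residual risk of the injections as the study's purpose. The safety endpoint is the incidence, severity and relationship of all AEs from injection to 6 months, and SAP 4.4 plans to tabulate local injection-site events against non-local ones. The reactions that the protocol itself calls transient or temporary are those most likely to begin and end with no scheduled AE enquiry in between. If they are asked about only some four weeks later, mild events may be forgotten, and onset, peak severity and duration have to be reconstructed. The local-event table would then tend to read low. With 25 subjects, one missed case changes the observed incidence by 4 percentage points (1/25).

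**Working it through.** The plan states no reaction rate and no capture rate, so it has no figure of its own to reproduce on this point. The check is mainly a comparison of sections.

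**1. Length of the first look-back.** Assumption: a month is 30 days.
- Schedule of Events, Month 1 ±3 days: 30 − 3 = 27 to 30 + 3 = 33 days.
- Protocol 7.6, all follow-up visits ±7 days: 30 − 7 = 23 to 30 + 7 = 37 days.

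The two windows differ and must be reconciled. Under either, the first AE enquiry after discharge looks back three to five weeks.

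**2. What could capture a reaction that starts after discharge and resolves within days.**
- *Reminder contact.* Protocol 7.5: "The subject should be contacted at least 48 hours prior to their scheduled assessments to be reminded of the required assessment". Its stated purposes are reminder, washout and scheduling. It need precede Month 1 by only 48 hours, and no AE question is described.
- *Report by the subject.* Requested in 7.4, but only for unexpected symptoms. Local pain and swelling are expected, so the request does not cover them.
- *Medication trace.* Rescue use is tracked daily (7.3.9.2), and the indication for a new medication becomes an AE unless the condition pre-existed (7.3.9.3). But paracetamol is both the rescue drug for osteoarthritis pain (7.3.9.2) and an option for injection-site pain (7.4), so a diary entry alone need not tell the two apart. Untreated swelling or stiffness leaves no entry.
- *Month 1 instruments.* The NRS asks about the last 24 hours (Appendix 1), and the physical evaluation (7.3.8) finds only what is still present.
- *Month 1 questioning.* Required by 8.1.1, and dependent on recall.

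**3. The recording rule.** Protocol 7.4 restricts post-treatment recording to unexpected signs and symptoms. Protocol 8.1.1 covers all AEs and names local pain and swelling. A site could follow 7.4 and leave out an event that 8.1.1 requires.

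**4. Illustration only.** Let p be the true proportion with a reaction and c the proportion of reactions captured; both are assumed. With N = 25, the expected number recorded is 25pc, and the chance of recording at least one is 1 − (1 − pc)^25.

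| p | c | Expected recorded | Chance of at least one |
|---|---|---|---|
| 5% | 100% | 1.25 | 72% |
| 5% | 25% | 0.31 | 27% |
| 10% | 100% | 2.5 | 93% |
| 10% | 50% | 1.25 | 72% |
| 10% | 25% | 0.62 | 47% |
| 20% | 100% | 5.0 | 99.6% |
| 20% | 25% | 1.25 | 72% |

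For example, at p = 10% and c = 50%, pc = 0.05 and 1 − 0.95^25 = 0.72.

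**5. The 1-week cells.** SAP 2.0 gives one visit schedule for the hip, shoulder and ankle studies, with no 1-week visit. The headings of SAP 4.1.3.3, 4.1.3.4 and 4.1.3.6 name 1, 3 and 6 months only. The DASH, PGA and medication analyses reuse the primary table format and so inherit the empty block.

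**The case against.** The case against is substantial in several respects.

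- A reader might infer that nobody contacts the subject before Month 1. Protocol 7.5 requires a reminder contact, so the supportable statement is that no scheduled *AE enquiry* takes place.
- A reader might infer that these reactions rest on recall alone. The Day 0 check, the invitation to report unexpected symptoms and the medication records are real routes, and a reaction visible before discharge or treated with a new drug may well be captured. They are partial, and weakest for mild, expected, untreated reactions.
- The diary form is not in the documents. One sentence describes it, so one can say that no symptom field is described, not that none exists.
- Sections 4.2 and 5.3 give no timing. That most such reactions resolve well before Month 1 is a fair reading of transient and temporary, but still a reading.
- Solicited daily symptoms are one way of collecting AEs, and nothing in the documents obliges the sponsor to use it.
- The 1-week cells might be taken as a sign of a dropped early visit. The documents do not support that: the cells concern efficacy results, no section describes such a visit, and the effect is a blank row and column.

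All of this limits the wording and the weight of the point. It does not supply a contemporaneous record of expected local reactions after discharge, nor does it resolve the difference between 7.4 and 8.1.1.

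**Conclusion.** The point holds as a gap in safety collection. Between discharge on Day 0 and Month 1 the plan schedules no AE enquiry and describes no symptom record. Its one prompt to the subject leaves out the reactions it expects. Following the plan as written would probably under-record mild local reactions and blur their severity and duration. This assumes that many such reactions start after discharge and resolve within days, and that recall over 23 to 37 days is imperfect. The amount lost cannot be derived from the documents, and the table above shows only how sensitive 25 subjects are to capture. The primary efficacy analysis is unaffected. The change is a cheap improvement worth making, not a defect that invalidates the study. The 1-week cells are a separate editorial slip and add no weight to the safety argument.

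**What to change.** 1. Add daily lines to the diary already dispensed at Baseline for study-shoulder injection-site pain, swelling, redness and stiffness (yes/no and severity), for Days 0-7. Extend the description in Protocol 7.3.9.6 to match, and have the entries reviewed at Month 1.
2. Reconcile Protocol 7.4 with 8.1.1 so that sites know whether expected reactions are recorded as AEs. Settle this first, because it determines how a positive diary entry is handled.
3. Reconcile the Month 1 window between the Schedule of Events and 7.6.
4. As an editorial correction only, delete the 1-week row block in SAP 4.1.2.1 and the 1-week column in SAP 4.1.3.4.

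**Cost.** Items 1 to 3 change the protocol. Under Protocol 13.3 that means an amendment signed by the investigator and the sponsor and submitted to the competent authority and the ethics committee. There is also a diary reprint, about a minute a day for a week for each subject, and somewhat higher recorded AE rates, which the report should attribute to solicited collection. No visit is added. Item 4 is a table-shell edit.
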